Contact for Clinical Queries	
[name]* Mersey & West Lancashire Teaching Hospitals NHS Trust, Diabetes Centre St Helens Hospital [name]
 
PA: [name] Email: [contact]

Sponsor	
The University of Liverpool is the research Sponsor for this Study. It is recognised that as an employee of the University the Chief Investigator has been delegated specific duties, as detailed in the Sponsorship Approval letter.
 
For further information regarding the sponsorship conditions, please contact:
 
[name] Senior Clinical Research Governance Manager [contact]

Key Protocol Contributors	
[name]* Email: [contact]
 
[name]* Email: [contact]

Committees	
This research proposal will be submitted to IRAS for independent ethical opinion by the Health Research Authority.
 
University of Liverpool Committee on Research Ethics** (online ethical approval process completed – confirmed that IRAS approval required)

*CV in appendix 1. ** University of Liverpool research ethics application project ID 13707.

Study Summary

Study Design	Quantitative feasibility study
Study Participants	People with type 2 diabetes mellitus
Planned Size of Sample (if applicable)	
120 people with type 2 diabetes.
 
Participants will be randomised across four groups, each with 30 participants.

Follow up duration (if applicable)	4 months
Planned Study Period	
This is educational research which is being undertaken to fulfil the requirements of a 3-year full time PhD with University of Liverpool commencing November 2023.
 
GANNT chart detailing timetable of research activities in appendix

	1.
Research Question/Aim(s)	
Aims
 
Using a quantitative approach this feasibility study aims to explore if patients who attend minimal aspects (10%) of diabetes self-management education (DSME) programmes gain clinically significant improvements in ability to self-care compared to those who do not attend. If the nationally accepted 60 % completion rate is as effective as 100% completion, and if
 
Research question
 
1. What is the impact of differing completion rates of DSME programmes on ability to self-care (primary outcome), diabetes distress and health related quality of life in type 2 diabetes.

Abstract

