5.2 Outcome

The primary outcome measure will be measured as:

- Change in self-care activities outcome measure (pre and post intervention) using the Diabetes Self-Management Questionnaire - Revised (DSMQ-R) scale (48).

Secondary outcome data will capture data on:

- Change in diabetes distress (pre and post intervention) using the Problem Areas in Diabetes (PAID) tool (49).
- Quality of life outcome measures (pre and post intervention) using the PROMIS-Global Health V1.2 scale (50).

Other preliminary data will explore whether deprivation and diabetes duration have any impact on PROMs across the four groups.

STUDY DESIGN AND METHODS OF DATA COLLECTION

This is a quantitative feasibility study focusing on the impact of differing completion rates of DSME programmes on psychometric outcomes pre and 4 months post intervention.

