6.2 Study processes

Screening and recruitment

Potentially eligible participants meeting the inclusion criteria and not excluded by exclusion criteria (outlined in section 8.1) who are either due to attend the diabetes centre for new patient clinic, have been referred for DSME intervention or are on the monthly shared care report for newly diagnosed type 2 diabetes requiring an offer of DSME will be screened for entry into the study and added to a screening log sheet (appendix 1). Potentially eligible participants due to attend new patient clinic will be invited into the study by NP clinic letter (appendix 1) with attached participant information sheet (PIS) (appendix 1). Letters will be posted ahead of their clinical appointment. For potential eligible participants identified through DSME referrals or the monthly shared care record report will be sent a telephone screening letter (Appendix 1) and PIS prior to meeting with the researcher. Study recruitment technique is outlined in further detail in section 8.2.2.

At the screening meeting potentially eligible participants will be asked to confirm they have read the PIS and invited to ask questions about the research. Where patients decline to take part in the research, they will be reassured this will not have any impact on their current or future treatment. Participants who give written informed consent will be enrolled onto the study. The researcher will utilise an informed consent checklist (Appendix 1) to ensure consistency and that all elements for informed consent have been completed. Participants will be consented for informing their GP, this is made clear in the PIS.

Visit 1

At enrolment baseline characteristics will be recorded from the electronic medical record, or where not available directly from the patient: NHS number, age, sex, ethnicity, diabetes duration, postcode, latest HbA_{1c}, prescribed glucose lowering agents, and a Charlson Comorbidity Index will be calculated. Postcode will be used to calculate indices of multiple deprivation (IMD) score.

Participants (n=120) will be randomised by permuted block strategy of 2:1 across four groups using an online randomisation software application designed for clinical trials (51,52). Due to the design of this study randomisation will not be blind to the researcher or participants. Group design will be as follows:

- Group 1: DSME 6 hours, 100% completed (completed).
- Group 2: DSME 3 hours 36 minutes, 60% completion (partial completion)

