8.2.21.2.2 Sample identification and technique

A convenience sample of 120 participants will be recruited for this study through three existing streams with potentially eligible participants added to the screening log sheet (appendix 1) and the pre-visit 1 section of the DIABETES-PRO study visit 1 pathway will be completed (appendix 1).

1. Clinic lists of new patients due to attend the diabetes centre at St Helens Hospital are available on the hospital patient administration system. The hospital electronic record will be used to screen for potentially eligible participants from the clinical list by the researcher. Potentially eligible participants due to attend new patient clinic will be invited into the study by letter (appendix 1, NP clinic screening letter) with attached PIS which will be posted ahead of their clinical appointment. On the day of their clinical appointment the researcher will meet potentially eligible participants to check they received the PIS and to answer any questions. Where potentially eligible participants agree they will be invited for

screening. Following screening, where eligible participants agree to be involved in the research and provide written informed consent, they will be enrolled in the study.

2. Patients who have been referred by their GP for DSME are called and offered education. Education referrals will be used to screen for potentially eligible participants from those awaiting a DSME appointment by the researcher. Potentially eligible participants will be asked as part of the DSME booking process if they would like information on the research. Where potential eligible participants agree a letter (appendix 1, telephone screening letter) will be sent out with a PIS and a screening appointment will be made with the researcher. Screening appointments will be offered either at the Diabetes Centre or as a home visit. Following screening, where eligible participants agree to be involved in the research and provide written informed consent, they will be enrolled in the study.

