3. Patients who have opted into data sharing and have been diagnosed with type 2 diabetes within the last month in primary care are reported via the shared care record, called and offered DSME. As part of this process potentially eligible participants will be screened and identified by the researcher. Potentially eligible participants will be asked as part of the DSME booking process if they would like information on the research. Where potential eligible participants agree a letter (appendix 1, telephone screening letter) will be sent out with a PIS and a screening appointment will be made with the researcher. Screening appointments will be offered either at the Diabetes Centre or as a home visit. Following screening, where eligible participants agree to be involved in the research and provide written informed consent, they will be enrolled in the study.

The researcher is employed as a diabetes clinical research fellow in the Diabetes Centre at St Helens Hospital and therefore already a member of the patients existing clinical team, however, is not providing direct clinical care to any potential participants. Clinical appointment lists and patient records will be obtained by the researcher in her existing NHS role. Sampling will continue until the required number of participants are recruited.

A screening and recruitment log will be stored in the study file and will include the following information: patient initials, screening outcome date of consent, if consent was refused, did/did not meet inclusion/exclusion criteria, date entered the study, unique identifier, randomisation group, study status (ongoing, withdrawn, completed, died) (70,71). A blank copy of the screening and recruitment log is included in appendix 1. Mersey and West Lancashire Teaching Hospital NHS Trust R&D department will be informed of all participants recruited to the DIABETES-PRO study.

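### Diabetes duration is recorded at baseline and varies widely by design, yet it is neither a stratification factor nor a covariate; adjusting for it would cost almost nothing and give a modest gain.

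*Combined protocol and SAP*

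**What the plan says.** Three streams feed one randomisation. Section 6.2 names them as the new patient clinic, DSME referrals and a monthly report of new diagnoses. The sample identification part of section 8.2 describes the streams:

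- **Stream 1:** "Clinic lists of new patients due to attend the diabetes centre at St Helens Hospital".
- **Stream 2:** people referred by their GP for DSME.
- **Stream 3:** people who "have been diagnosed with type 2 diabetes within the last month in primary care".

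Section 8.1 sets no limit on diabetes duration. It excludes only those who had structured education in the previous 12 months.

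On allocation, section 6.2 (Visit 1) states that participants "will be randomised by permuted block strategy of 2:1 across four groups using an online randomisation software application designed for clinical trials". It names no stratification or minimisation factor. The Study Summary states: "Participants will be randomised across four groups, each with 30 participants".

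On analysis, section 6.4 compares before-after differences across the four groups by ANOVA at a 5% alpha and names no covariate. It also rejects intention to treat and withdraws the results of participants who do not complete their allocated amount of DSME.

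Duration is among the baseline items listed in section 6.2, and section 5.2 adds: "Other preliminary data will explore whether deprivation and diabetes duration have any impact on PROMs across the four groups". No method is given for that exploration.

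**The concern.** The protocol itself treats diabetes duration as something that may influence the outcomes, and the recruitment streams make it vary widely. With about 30 per group, simple chance can put noticeably more newly diagnosed people in one group than in another. If such people change differently over four months whatever education they receive, part of an observed group difference would reflect case mix. An ANOVA without covariates does nothing to correct the realised estimate.

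This matters because section 8.2.1 justifies the sample as adequate for estimating effect sizes and informing later research. The aims put two pairwise questions (10% v no education, and 60% v 100%), each resting on about 30 v 30. The planned look at duration would also have uneven cells.

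**Working it through.** **Plan's own figure.** 4 × 30 = 120, as stated. If 20% dropout is assumed (the rate is not stated; this is the edge of the green retention band in Table 3), 24 / 0.80 = 30 per group, which matches the lower end of the 24-50 range in section 8.2.1. A 2:1 ratio does not give 30 per group: 2:1:1:1 gives 48/24/24/24 and 2:2:1:1 gives 40/40/20/20. What follows takes the stated 30 per group.

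**Inputs not in the documents.** Two are needed, and both are assumptions shown over a range:
- the share newly diagnosed, 20% to 80%. Section 8.2.1 gives 86 new diagnoses and 24 DSME referrals a month, but that is supply rather than enrolment, and clinic volume is missing;
- the gap in mean four-month change between newly diagnosed and other participants, 0.3 to 0.8 SD.

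**Step 1: chance imbalance.** For two groups of n = 30 drawn from N = 120 with share p, the SD of the difference in shares is √[2p(1−p)N / (n(N−1))]. At p = 0.5 this is √[0.5 × 120 / (30 × 119)] = 0.130. At p = 0.2 it is √[0.32 × 120 / (30 × 119)] = 0.104. Exact hypergeometric probabilities for one pair, with simulation for at least one of the two pairs, give:

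| Share newly diagnosed | SD of difference | ≥10 points | ≥20 points | ≥30 points | ≥20 points in at least one of the two pairs |
|---|---|---|---|---|---|
| 20% or 80% | 10.4 points | 42% | 7.6% | 0.6% | 15% |
| 30% or 70% | 11.9 points | 48% | 12.2% | 1.6% | 23% |
| 50% | 13.0 points | 52% | 15.7% | 2.8% | 29% |

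Twenty points is 6 people in 30.

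**Step 2: effect on the estimate.** Shift = imbalance × gap. The standard error of a 30 v 30 difference is SD × √(2/30) = 0.258 SD. The yardstick is the 0.5 SD rule that section 6.4 uses for the MCID of DSMQ-R and PAID. For a 20-point imbalance:

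| Assumed gap | Shift | In SEs | Share of 0.5 SD |
|---|---|---|---|
| 0.3 SD | 0.06 SD | 0.23 | 12% |
| 0.5 SD | 0.10 SD | 0.39 | 20% |
| 0.8 SD | 0.16 SD | 0.62 | 32% |

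A typical imbalance (one SD, 10 to 13 points) with a 0.5 SD gap shifts the estimate by about 0.05 to 0.065 SD.

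**Step 3: error rate.** Simulated t-tests at a two-sided 5% level (sidedness is assumed), a 50% share and gaps of 0.3 to 0.8 SD give an overall type I error of 4.7% to 5.1%. Given a realised 20-point imbalance, it is about 5.4%, 6.0% and 7.2% for the three gaps.

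**Step 4: precision gained by adjustment.** With a 50% share and a 0.5 SD gap, duration explains about 0.25 × 0.5² = 0.0625 of the variance. The SE falls from 0.258 to about 0.258 × √(1 − 0.0625) = 0.250 SD, roughly 3%.

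**Step 5: what stratified blocks would do.** With equal allocation in blocks of 4 within two strata, any two groups as randomised differ by at most 1 newly diagnosed person (3.3 points). That is 0.033 × 0.5 = 0.017 SD at the 0.5 SD gap. With blocks of 8 the limit is 2 people (6.7 points).

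**Step 6: the duration exploration.** At a 30% share each group has 9 newly diagnosed people on average; the median smallest and largest groups hold 7 and 11. The difference detectable with 80% power is (1.96 + 0.84) × √(2/m), which is 1.32 SD for 9 v 9 against 0.72 SD for 30 v 30.

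**The case against.** The strongest reply is that randomisation already deals with this. The comparison is unbiased over repeated allocations, its standard error includes chance imbalance in prognostic factors, and overall type I error stays near 5%. This stands. A reader might infer that the unstratified design biases the trial or makes its tests invalid; the documents do not support that.

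The size rests on two assumed inputs, and no passage says that newly diagnosed people change differently over four months. This also stands, and it is why ranges are given. The idea that longer-standing patients carry over habits from earlier education is weak locally: the Background reports 9.1% attending DSME within 12 months of diagnosis and 12.6% of starters completing.

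A reader might also infer that stratifying by recruitment stream would remove nearly all of the problem. That does not hold, for two reasons. Primary care refers directly into DSME, which is recommended at diagnosis, so stream 2 can also contain newly diagnosed people, and route is a poor proxy for duration. And balance set at randomisation is not protected once section 6.4 withdraws incomplete attenders.

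Finally, this is an unpowered feasibility study with deliberately mixed streams, whose progression criteria are recruitment and retention. Section 6.4 specifies a four-group ANOVA; the two pairs come from the aims. This limits the priority of the point. It does not remove it, because the plan still intends to estimate and test group differences, and the covariate is already collected.

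**Conclusion.** A minor point that holds as a nearly free improvement. Duration is mixed by design, recorded at baseline and of declared interest, but unused in allocation and in the main comparison. On the assumed ranges, a 20-point imbalance in a given pair has about an 8% to 16% chance and would move the estimate by 0.06 to 0.16 SD, less than one standard error (about 0.26 SD). The average precision gain from adjustment is small, about 3% of the SE at a 50% share and a 0.5 SD gap. The main benefit is that a realised imbalance in duration is accounted for by a rule fixed in advance.

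The duration exploration is limited more by small cells than by imbalance, and stratification would not enlarge them. The absence of a stratification factor is judged from the protocol text alone, because Appendix 1 is a separate document that was not available.

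**What to change.** In section 6.4, prespecify diabetes duration at enrolment as a covariate in the group comparison of change, either as recent diagnosis v longer or as a continuous variable. Choose the form before data are seen, and use the same term in the duration exploration of section 5.2. The cost is one model term; no new data are needed and N stays at 120. The adjustment addresses duration imbalance among those analysed, but it does not repair other selection caused by withdrawing incomplete attenders.

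Optionally, stratify the permuted blocks by the same duration cut rather than by recruitment stream. The natural moment is when the list is set up and the 2:1 wording is reconciled with four groups of 30, which has to be done anyway. The cost is one setting in the randomisation service and two lists instead of one, so final group sizes may differ from 30 by one or two.

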- Group 3: DSME 36 minutes, 10% of content (attended)
- Group 4: Delayed education (education not offered, not attended, or declined)

DSME programme overview is provided in appendix 1 giving a broad overview of DSME content by programme completion status. Local demographic data suggests that of the local population 46.4% are living in the most deprived neighbourhoods within the UK (9). Of the local population 19.3% have a reading age of 9-11 or below (53,54), are classed as being functionally illiterate and are therefore likely to struggle reading a paper questionnaire. Verbal support for completing the PROMs will be offered by the researcher to ensure participants from lower socioeconomic backgrounds are not excluded from participating in the DIABETES PRO study as they are evidenced to make up a larger proportion of people with diabetes (55-57). Support will be limited to reading the questions verbatim.

Participants will be asked to complete three psychometric tests measuring self-care activities, diabetes distress and quality of life using the following validated tools: Diabetes Self-Management Questionnaire-Revised (DSMQ-R)(48), Problem Areas in Diabetes (PAID) scale (49) and the Patient Reported Outcome Measures Information System (PROMIS) Global Health scale v1.2 (50) (appendix 1).

Participants in groups 1, 2 and 3 will be asked to book a DSME session with the researcher, typically this should be no longer than 3 weeks from study enrolment. Research group DSME programmes (intervention) will be run by the researcher separate to routine patient DSME to minimise disruption of participants leaving part way through on patients.

Participants randomised to group 4, delayed education will not be required to attend DSME as part of the DIABETES PRO study. Collected data will be collected and managed using Research Electronic Data Capture (REDCap) electronic data capture tools. A REDCap data collection tool has been included in Appendix 1 for reference. REDCap is a secure, web-based software platform designed to support data capture for research studies, providing an intuitive interface for validated data capture; audit trails for tracking data manipulation and export procedures; automated export procedures for seamless data downloads to common statistical packages; and procedures for data integration and interoperability with external sources (58,59) (see section 3.6 for further details).

Visit 2

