6.4 Data Analysis

Descriptive analysis will be completed for all demographic data presenting continuous variables as means \pm standard deviation and categorical variables as numbers (%). Data will be tested for normality using a Shapiro-Wilk test and subject to visual inspection of histograms and normal Q-Q plots.

Psychometric outcomes will include the Diabetes Self-Management Questionnaire-Revised (DSMQ-R)(48), Problem Areas in Diabetes (PAID) scale (49) and the Patient reported outcome measures information system (PROMIS) Global Health scale v1.2 (50). Data will be treated as continuous and analysis of the difference in the mean before and after intervention will be conducted using an analysis of variance (ANOVA) test to check for statistical and clinical difference in the mean across the four groups.

Statistical analysis will be conducted using IBM® SPSS® Premium 29 with support from University of Liverpool statisticians. The alpha level will be set at 5% for statistical significance.

Whilst a statistically significant difference is desirable, it is important to understand what would represent a meaningful clinical change for a patient. As such the minimal clinically important difference (MCID) will be reported to measure the smallest difference in which the patient would perceive a benefit (61–64). Where the MCID is not published this will be calculated using a distribution-based derivation using 0.5 SD of the observed change in PROM score (62,65). Whilst this approach is not without its limitations (61,63) no consensus on the ideal means of determining the MCID is available (63). A systematic review concluded that 0.5 SD of the observed change approximated the published MCID in the majority of cases popularising this derivation in the literature (65).

MCID will be classed as >2 T-score points for the PROMIS Global Health v1.2 (66) in which physical health and mental health are given separate T-scores with a 95% confidence interval. The MCID will be calculated for PAID and DSMQ-R.

Recruitment of participants and the number of dropouts will be reported descriptively (frequencies and percentages). Due to the aims of this study considering differing completion levels of DSME, intention to treat analysis will not be used. Where participants allocated to a group do not fully complete the required amount of DSME there results would be withdrawn from the final analysis.

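### As written, Visit 1 puts open randomisation before the baseline questionnaires and does not say they are finished before allocation is disclosed, so the primary change score is open to an avoidable bias

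*Combined protocol and SAP*

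**What the plan says.** Section 6.2 (Visit 1) sets out the visit in this order.

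1. Data from the record: "At enrolment baseline characteristics will be recorded from the electronic medical record".
2. Allocation: participants are "randomised by permuted block strategy of 2:1 across four groups", followed by "Due to the design of this study randomisation will not be blind to the researcher or participants" and the list of four groups (full programme, 60%, 10%, delayed education).
3. Questionnaires: "Participants will be asked to complete three psychometric tests measuring self-care activities, diabetes distress and quality of life using the following validated tools".
4. Booking by group: "Participants in groups 1, 2 and 3 will be asked to book a DSME session with the researcher".

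The primary outcome in section 5.2 is "Change in self-care activities outcome measure (pre and post intervention) using the Diabetes Self-Management Questionnaire - Revised (DSMQ-R) scale". Section 6.4 plans that "analysis of the difference in the mean before and after intervention will be conducted using an analysis of variance (ANOVA) test" across the four groups, at a 5% alpha level, and mentions no adjustment for baseline. For DSMQ-R and PAID the same section sets the MCID at half the SD of the observed change.

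The Visit 3 text in section 6.2 calls the Visit 1 questionnaires the baseline tests. Sections 6.2 and 9.1 and Table 5 limit the researcher's help to reading the items word for word. Section 6.3 says that pathway checklists govern each visit, but these sit in a separately held appendix. The body of the flow chart (Figure 1) is also not visible.

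**The concern.** All three instruments are self-reported, and the groups differ in ways a participant will notice: six hours of education, leaving after 3 hours 36 minutes, leaving after 36 minutes, or waiting until the end of the study. Someone who has just learned their group may answer items on distress or self-care differently from someone who has not. Where that reaction differs between groups, the baseline no longer has the balance that randomisation should give it.

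The analysis has no protection against this. A change score subtracts the baseline, so a shift confined to baseline goes in full into the group contrast with its sign reversed. Verbatim reading limits the researcher's influence on the answers, but does nothing about what the participant already knows. Follow-up in this design is unavoidably open, whereas the baseline need not be. The study is meant to estimate effect sizes (section 8.2.1) and to test the procedures of a later full trial, so the order of Visit 1 would probably carry forward.

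**Working it through.** **Order of steps.** In section 6.2 the first, second and fourth items above fall in natural working order: record data, allocate, book according to group. A site would reasonably read the third item as falling where it is written. No linking words fix the sequence, and no sentence puts the questionnaires on either side of disclosure.

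**Inputs from the plan.** Four groups of 30 (section 8.2.1: 4 × 30 = 120, which reproduces the stated total); ANOVA on the before-after difference, 5% level and MCID = 0.5 SD of change (section 6.4).

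**Assumptions.** The documents give no SD, no pre-post correlation and no size for any shift. I assume no true effect, a shift of b (in SD of change) at baseline in one group only, none of it persisting to follow-up, and no dropout.

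**Error rate of the planned test.** With one of four groups displaced by b, the noncentrality is λ = n × (1 − 1/4) × b² = 30 × 0.75 × b² = 22.5 b². The test has 3 and 4 × 30 − 4 = 116 degrees of freedom and a 5% critical value of 2.683. The rejection rate is the upper tail of the noncentral F beyond that value. The share of the MCID is b / 0.5.

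| b (SD of change) | λ | Rejection rate | Share of MCID |
|---|---|---|---|
| 0 | 0 | 5.0% | 0% |
| 0.1 | 0.225 | 6.3% | 20% |
| 0.2 | 0.900 | 10.6% | 40% |
| 0.3 | 2.025 | 18.9% | 60% |

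**Persistence.** If a fraction p of the shift is still present at follow-up, the bias in the change score is (1 − p)b. With b = 0.2 and p = 0.5 it is 0.1 SD, which gives 6.3%. With p = 1 it cancels and the rate is 5%.

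**Sensitivity to scale.** If b is instead in SD of the score, then SD of change = √(2(1 − r)), where r is the pre-post correlation. At r = 0.5 this is 1.000 and the table is unchanged. At r = 0.7 it is 0.775, so b = 0.2 becomes 0.2 / 0.775 = 0.258 SD of change (52% of the MCID), with λ = 22.5 × 0.0667 = 1.5 and a rate of 14.9%.

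**Would baseline adjustment cure it?** Adjustment leaves a bias of about r × b for a shift confined to baseline. With b = 0.2 SD of the score, that is 0.10 SD at r = 0.5 (rate 6.8%) and 0.14 SD at r = 0.7 (rate 10.4%). It lessens the bias and does not remove it.

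**After the fix.** With the questionnaires completed before disclosure, b = 0 by design, and the baseline part of the bias is zero.

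**The case against.** The strongest reply is that paragraph order is not a timing rule. Visit 1 mixes group definitions, local literacy figures, booking and data-capture details, and the randomisation sentence can be read as design description. The questionnaires are called baseline tests, and the checklist may already put them first. This stands as a limit on the point: the order is inferred, and practice may be sound. It does not remove the point, because the word baseline separates Visit 1 from Visit 3 without saying which side of disclosure it falls on, and the protocol should state the order itself.

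A reader might infer that the primary outcome is biased. The documents do not support that. Bias needs a reaction that differs by group, and neither its size nor its direction is given. It would also cancel from the change score if it lasted unchanged to follow-up. Nor should group 4 be thought of as told they will get no education: their education is delayed, and groups 2, 3 and 4 are all offered the full programme at the end.

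It can also be said that section 6.1 describes an unpowered feasibility study, so an inflated error rate matters less than in a confirmatory trial. That is fair and keeps the weight moderate, but section 6.4 still tests at 5%, and the estimates are meant to inform later research.

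**Conclusion.** The point holds as a risk in the written procedure. Section 6.2 places open allocation ahead of the baseline questionnaires, and no available text requires them to be completed before disclosure. If that order is followed, the change score is exposed to whatever part of an allocation-driven shift affects baseline and fades by follow-up.

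The size is illustrative only. Over assumed shifts of 0.1 to 0.3 SD of change in one group, the planned ANOVA rejects in about 6% to 19% of null trials instead of 5%, and the false difference is 20% to 60% of the plan's own MCID. At the low end the effect is small. This is a worthwhile improvement that costs almost nothing. It is not evidence that the results will be wrong.

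**What to change.** In section 6.2 (Visit 1), move the questionnaire paragraph ahead of the randomisation paragraph and add a sentence such as: DSMQ-R, PAID and PROMIS are completed and dated before the randomisation service is opened; allocation is then revealed. Confirm that the Visit 1 checklist and the flow chart show the same order, and amend them if they do not. Record the time of questionnaire completion and of randomisation, so that adherence can be reported.

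The cost is one reordered paragraph and one checklist line, within the same visit and with no extra staff or participants. If the sponsor already works in this order, the change only puts it on record. The fix deals with the baseline part alone. Self-report at follow-up stays open-label and should be reported as a limitation.
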